7.3.4 Analysis Methods-Secondary endpoints

Average change of GI severity scores from Day 0 to Day 10, as measured by the total change of GSRS scores from Day 0 over the first 10 days (Day 1 to Day 10), divided by total number of days with GSRS recorded

Average change of GI severity scores from Day 0 (baseline) to Day 10 will be calculated as the sum of changes from baseline in GSRS score over the first 10 days divided by the total number of days with GSRS recorded. The average change will be summarized by treatment and analyzed using an analysis of covariance (ANCOVA) model adjusted for age, weight and baseline GSRS score. To adjust for missing data, a weight defined as the proportion of days with GSRS score recorded will be assigned to each subject. The difference of the average GSRS score between the two treatment arms will be tested.

Normality assumption of the ANCOVA will be tested. If violated, a rank based ANCOVA will be used.

A sensitivity analysis using a mixed-effects model for repeated measures (MMRM) for the change of the GSRS score from baseline will be conducted. The model will be adjusted for age, weight and baseline GSRS score as continuous variables, and will have unstructured variance-covariance structure. The primary test based on the model will be the test of the null hypothesis of no difference between the two treatment groups in the average change from Day 0 (baseline) between Day 1 and Day 10. Trajectory plot of the change in GSRS score with 95% CIs, by time and by treatment group, estimated from the model, will be presented. Trajectory plot of the mean change in GSRS score by day will be presented as well.

Depending on the GSRS, study treatment and/or DMF compliance, sensitivity analysis may be performed using MMRM in patients with a compliance rate from Day 0 to Day 10 above a certain threshold.

Average change of GI severity scores from Day 0 to Week 10 as measured by total change of GSRS scores from Day 0 over the first 10 weeks (Day 1 to Week 10) divided by total number of days with GSRS recorded

Average change of GI severity scores from Day 0 (baseline) to Week 10 will be calculated as the sum of changes from baseline in GSRS score over the first 10 weeks divided by the total number of days with GSRS recorded. This endpoint will be analyzed by the MMRM as in the analysis of the above endpoint. Sensitivity analyses using ANCOVA model for the average change may be performed. Trajectory plots of mean change and the model based estimated mean change from baseline in GSRS score (with 95% CIs), by time and by treatment group, will be presented.

Time to first worsening of GSRS in GI severity

The GI severity is worsened if the GSRS score increases from baseline (Day 0). Time to first worsening of GSRS in GI severity is defined as the number of days from Day 0 to the first date with a worsened GSRS score. If a patient does not experience any worsening from Day 0 to Day 10, his/her time to first worsening will be censored at Day 10 or the day of study treatment (Montelukast/PBO) discontinuation, whichever comes first.

Time to the first worsening of GSRS by treatment arm will be analyzed using the Kaplan-Meier method and the Cox's proportional hazards model adjusted for age, weight and baseline GSRS score. If the proportionality assumption does not hold, a log-rank test will be used.

Time to recovery to Day 0 GSRS score from the last occurrence of the worst score in GI severity

The GI severity is recovered to Day 0 GSRS score if the GSRS score is smaller than or equal to the Day 0 score. Time to recovery to Day 0 score from the last occurrence of the worst score is defined as the date of recovery minus the date of the last occurrence of the worst score. If a patient does not experience a worsening in GSRS score, the last occurrence of the worst score is Day 0 and time to recovery is 1. If a patient experiences a worsening of GSRS score but does not experience a recovery before Week 8, his/her time to recovery will be censored at Week 8 or the day of study treatment (Montelukast/PBO) discontinuation or the day of switching to other GI medications listed in I/E criterion 8, whichever comes first.

Time to recovery to Day 0 GSRS score from the last occurrence of the worst score will be analyzed using the Kaplan-Meier method and the Cox's proportional hazards model.

Average change of GSRS score from Day 0 to Week 1, 2, 3, 4, 5, 6 and 8

Average change of GSRS score from baseline (Day 0) to Week 1, 2, 3, 4, 5, 6 and 8 will be summarized; a repeated measures model for the change of the GSRS score from baseline, adjusted for age, weight and baseline GSRS score, will be used to estimate effect at each time point. Sensitivity analyses using ANCOVA model for the average change may be performed.

Average change of GSRS score from Day 0 to 72 hours from the initiation of randomized study treatment

Average change of GSRS score from baseline (Day 0) to 72 hours (Day 3) from the initiation of randomized study treatment will be summarized and analyzed by the repeated measures method. No sensitivity analysis will be performed.

Proportion of subjects who take GI symptomatic therapy during the study

From Day 10 onward, subjects are allowed to use symptomatic therapy to treat DMFrelated GI events. The proportion of subjects who take GI symptomatic therapy from Day 10 to Week 10 will be summarized by treatment and analyzed using the Chi-squared test.

[figure not shown]
Percentage of subjects who discontinue DMF therapy due to the GI-related adverse events from Day 0 to Week 10

The proportion of subjects who discontinue DMF due to the GI-related adverse events from Day 0 to Week 10 will be summarized by treatment and analyzed using the Chi-squared test.

Proportion of subjects who experience flushing events

The proportion of subjects who experience flushing events from Day 0 to Week 10 will be summarized for the modified ITT population by treatment group and analyzed using the Chi-squared test. Flushing event as defined as an event coded to any of the following preferred terms: Flushing, Hot flush (under SOC of Vascular disorders), Erythema, Generalized erythema, Skin burning sensation (under SOC of Skin and subcutaneous tissue disorders), Burning sensation (under SOC of Nervous system disorders), Feeling hot (under SOC of General disorders and Administration site conditions), Hyperaemia (under SOC of Vascular disorders).

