7.2.3. Randomization Visit

Subjects will return to the study site for a recheck of eligibility criteria (only GSRS scores and concomitant medications/procedures will be checked). Individuals with GSRS score of ≥ 5 in 1 question for 1 day, a GSRS score of ≥ 4 in 1 question for 2 consecutive days, or a GSRS score of ≥ 3 in 1 question for 3 consecutive days during the Screening Period will be discontinued and counted as screen failures. Subjects will be required to be $\geq 75\%$ compliant in the 14 days prior to randomization to remain eligible to participate in the study, and sites should continue to monitor eDiary compliance throughout the study. Concomitant medications/procedures will be checked to ensure compliance with study restrictions. Once eligibility has been rechecked and it is confirmed that a subject is eligible to continue on the study, blood samples will be collected for the assessment of clinical laboratory parameters and serum biomarkers (optional). Eligible subjects will be randomized and provided with blinded randomized study treatment (montelukast or placebo) at this time.

Eligible subjects will receive commercial DMF through their specialty pharmacy or, in the case of insufficient insurance coverage, through the Biogen Patient Services Free Drug Program, for up to 14 weeks. The Investigator will submit the DMF prescription to Patient Services during the Screening Visit, and DMF will be shipped directly to subjects.

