12. WITHDRAWAL OF SUBJECTS FROM STUDY TREATMENT **AND/OR THE STUDY**

A subject *must* permanently discontinue study treatment and be withdrawn from the study for any of the following reasons:

- Failure to meet the required eDiary compliance criteria (\geq 75%) in the 14 days prior to randomization.
- Failure to meet the GSRS score criteria during the DMF-GI Monitoring Period. •
- The subject experiences a medical emergency that necessitates permanent discontinuation of study treatment.
- The subject uses prohibited concomitant medications (as outlined in Sections 1 and 10.3.1).
- The subject withdraws consent.

Protocol 109MS414

- At the discretion of the Investigator for medical reasons or for noncompliance.
- The subject has a concurrent illness or injury, or abuses alcohol or drugs to the extent that, in the judgment of the Investigator and/or Sponsor, it would affect assessments of clinical status to a significant degree.

The reason for discontinuation of study treatment and withdrawal from the study must be recorded in the subject's CRF.

Subjects who discontinue study treatment will be withdrawn from the study. Whenever possible, subjects who prematurely discontinue study treatment should complete an ET Visit (undergoing the same assessments as the Week 10 Visit).

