7 STATISTICAL ANALYSIS METHODS

The statistical software, SAS[®], will be used for all summaries and statistical analyses.

Summary statistics will be used throughout. For continuous endpoints, the summary statistics will generally include: the number of subjects with data, mean, standard deviation (SD), median, 25th and 75th percentile (Q1, Q3), minimum and maximum. For categorical endpoints, the summary statistics will generally include: number of patients randomized and dosed, the number of patients with data, and the number and percent of subjects with data in each category.

All statistical tests will be 2-sided with a type I error rate of 5%, unless otherwise specified.

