7.1 Analysis population

7.1.1 Modified ITT population

The modified intent-to-treat (modified ITT) population consists of all patients who were randomized, received at least one dose of DMF treatment, received at least one dose of study treatment (Montelukast or placebo) on/after the first DMF dose date, and had at least one GSRS score measurement during the Day 1 - Day 10 period.

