7.3.3 Analysis Methods-Primary endpoints

Proportion of subjects with a worsening in the severity of GI AEs, measured by the average change from Day 0 to Day 10 in GSRS score

The average change of the GSRS score from Day 0 (baseline) to Day 10 will be calculated as the sum of changes from baseline in GSRS score over the first 10 days divided by the total number of days with GSRS recorded. A positive average change of GSRS score from Day 0 to Day 10 means a patient has an overall worsened GI severity. A negative average change of GSRS score from Day 0 to Day 10 means an overall improved GI severity.

The proportion of subjects with worsening will be summarized by treatment and will be estimated from a weighted logistic regression model adjusted for age, weight and baseline GSRS score as continuous variables. Each patient included in this model will be assigned a weight defined as the proportion of days with GSRS score recorded. The weight is used to account for the missing data when patients do not report the GSRS score. The odds ratio (OR) for the Montelukast treatment group compared to placebo will be reported. The corresponding P-value from the likelihood ratio test of the null hypothesis that the OR = 1 will be given. Profile likelihood 95% profile likelihood confidence interval (CIs) will be given for the odds ratio.

SAS procedure "genmod" or SAS procedure "logistic" will be used to perform the primary analysis. Below is the example of SAS procedure genmod:

```
proc genmod data=ds1 descending;*assuming ds1 is the name of the data
set
    class trtpn;
    model worsec = trtpn weight age gsrsb/dist=bin link=logit lrci;
    weight pdays;
    lsmeans trtpn / pdiff cl;
    contrast "difference between treatments" trtpn -1 1;
run;
```

Depending on the GSRS, study treatment and/or the DMF compliance, sensitivity analysis may be performed among patients with a compliance rate from Day 0 to Day 10 above a certain threshold. A chi-squared test for the difference in the rate of worsening between the two treatment groups may also be performed.

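### Time to first worsening counts days with no diary entry as event-free up to Day 10, which lowers the worsening rate and shifts the hazard ratio if diary stopping differs by arm

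*Combined protocol and SAP*

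**What the plan says.** SAP 7.3.4 defines time to first worsening as "the number of days from Day 0 to the first date with a worsened GSRS score". For a subject without one, "his/her time to first worsening will be censored at Day 10 or the day of study treatment (Montelukast/PBO) discontinuation, whichever comes first". The analysis is Kaplan-Meier plus a "Cox's proportional hazards model adjusted for age, weight and baseline GSRS score". No weight for unrecorded days is stated.

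For time to recovery, the same section censors a subject who worsened and did not recover at the earliest of Week 8, stopping study treatment, or switching to a listed GI medication. The last diary entry is again absent.

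Other parts of the plan bear on how much diary data there will be:

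- **Entry to the analysis.** SAP 7.1.1 requires that the subject "had at least one GSRS score measurement during the Day 1 - Day 10 period". Nine of the ten days may be blank.
- **Diary compliance.** Protocol 7.2.3 requires subjects to be at least 75% "compliant in the 14 days prior to randomization to remain eligible to participate in the study". After randomization, sites monitor compliance, but no minimum applies.
- **Stopping treatment.** Protocol 12: "Subjects who discontinue study treatment will be withdrawn from the study".
- **Missing days elsewhere.** For the primary logistic model, SAP 7.3.3 says: "Each patient included in this model will be assigned a weight defined as the proportion of days with GSRS score recorded". The Day 10 ANCOVA in SAP 7.3.4 has the same weight. Tables 14 and 17 repeat these two analyses in compliant subjects. Time to first worsening (Table 19) has neither provision.

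**The concern.** A worsening can be seen only on a day with a GSRS entry. Take a subject who records Day 1 without worsening, then stops the diary and keeps taking the tablets. No worsening is ever recorded and treatment is not discontinued, so the rule censors at Day 10. Nine unobserved days enter the risk sets as follow-up known to be free of the event.

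Two consequences follow. The Kaplan-Meier worsening rate is too low in any arm where this happens. If one arm stops its diaries more often, that arm appears to worsen less, and the hazard ratio moves even when the treatments do not differ.

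For recovery the event is favourable, so the direction reverses. Unrecorded days count as not recovered, and an arm that stops its diaries more often appears to recover more slowly. The span is up to Week 8 rather than Day 10.

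**Working it through.** **The plan's own figure.** No design figure is stated for this endpoint. The only one is the primary sample size in SAP 6. For 40% vs 70%, two-sided 5%, 80% power:

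- Uncorrected n = (1.96 × √(2 × 0.55 × 0.45) + 0.8416 × √(0.24 + 0.21))² / 0.30² = 42 per arm.
- With continuity correction, (42/4) × (1 + √(1 + 4/(42 × 0.30)))² = 48.4, so 49 per arm.
- 49/0.85 = 57.6, so 58 per arm, or 116 in total against 118 stated.

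The plan's figure is reproduced to within 2 patients. It does not depend on the censoring rule.

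**Assumptions, because the documents give no rates.** The daily hazard of worsening is h = 0.10 on Days 1-10, and a share f of an arm stops the diary while on treatment. The last entry is uniform on Days 1-9 and unrelated to symptoms. Hazard ratios are montelukast over placebo.

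**Step 1: worsening rate.** True Day 10 risk = 1 − 0.9¹⁰ = 0.651. A stopper's worsening is seen with probability 1 − (1/9) × Σ 0.9ˢ for s = 1 to 9, which is 1 − 0.613 = 0.387. Under the stated rule, apparent risk = (1 − f) × 0.651 + f × 0.387 = 0.651 − 0.264f.

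| f | Stated rule | Censored at last entry |
|---|---|---|
| 10% | 62% | 65% |
| 25% | 59% | 65% |
| 40% | 55% | 65% |

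**Step 2: hazard ratio with no true effect.** The share still recording on Day d is W(d) = 1 − f(d − 1)/9. Expected recorded events are e(d) = W(d) × 0.9^(d−1) × 0.10.

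- Stated rule: at risk R(d) = 1 − Σ e(j) for j < d.
- Last entry: at risk W(d) × 0.9^(d−1), so e(d)/R(d) = 0.10 every day in both arms.

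With 30% stopping on placebo and 10% on montelukast, Day 1 hazards are equal. By Day 10 the stated rule gives 0.0271/0.4549 = 0.060 on placebo and 0.0349/0.4099 = 0.085 on montelukast. Solving the Cox score equation over the ten days gives:

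| Stopping, placebo vs montelukast | Stated rule | Last entry |
|---|---|---|
| 15% vs 15% | 1.00 | 1.00 |
| 15% vs 5% | 1.06 | 1.00 |
| 25% vs 5% | 1.12 | 1.00 |
| 30% vs 10% | 1.12 | 1.00 |

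**Step 3: other assumptions.** At true Day 10 worsening of 40%, 60% or 80%, the 25% vs 5% case gives 1.11-1.12, and the reverse (5% vs 25%) gives 0.90. If all stopping follows Day 1 (25% vs 5%, true worsening 60%), the hazard ratio is 1.29. With a real effect (60% vs 30% worsening; daily hazards 0.0876 and 0.0350, ratio 0.40), equal 15% stopping gives 0.405, 25% vs 5% gives 0.45, and 5% vs 25% gives 0.36.

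**Step 4: stopping caused by symptoms.** Suppose a share f stops on the day of worsening, so that the worsening is never recorded. Censoring at the last entry then gives an observed daily hazard of (1 − f)h/(1 − fh).

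- 30% vs 10%: placebo 0.070/0.970 = 0.0722, montelukast 0.090/0.990 = 0.0909. Ratio 1.26, against about 1.4 under the stated rule.
- 15% vs 5%: placebo 0.085/0.985 = 0.0863, montelukast 0.095/0.995 = 0.0955. Ratio 1.11, against about 1.17 under the stated rule.

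Last-entry censoring reduces this bias but does not remove it.

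**Recovery.** Its direction follows from the definition. Its size was not calculated.

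**The case against.** Several points stand on the other side.

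- **The affected group is narrow.** Subjects who stop study treatment are withdrawn and are already censored that day. Only those who stop the diary alone are carried forward.
- **There are partial safeguards.** Subjects had to show 75% compliance before randomization, sites monitor the diary, the investigator may withdraw for noncompliance, and Table 11.1 summarises GSRS compliance. These make 40% stopping look extreme. They would expose poor recording but do not change the censoring date.
- **The shift is small against the noise.** SAP 5 closes enrolment at about 60 dosed. If 60% have events (36), the standard error of the log hazard ratio is about 2/√36 = 0.33, and a null 95% interval runs from about 0.52 to 1.92. A hazard ratio of 1.06 to 1.12 is a shift of 0.17 to 0.34 standard errors.

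A reader might go further in three ways that the documents do not support:

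- **That the primary result is affected.** The primary model uses the average change, with a weight for recorded days, and does not use this rule.
- **That the hazard ratio is biased whenever diaries stop.** With equal stopping it barely moves (0.405 against 0.40).
- **That tied daily times will distort the hazard ratio through a software default.** SAP 7 names SAS but no Cox procedure, tie option or default, so that claim has no footing here.

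**Conclusion.** The rule is wrong as written. Read literally, it treats unobserved days as observed and event-free, and the weights and compliance-restricted tables used elsewhere in the SAP do not reach this endpoint. The direction for the worsening rate is certain: downward. The hazard ratio is distorted only when stopping differs by arm, and the direction depends on which arm stops more.

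Under the assumed 10% daily hazard and random stopping, 10% to 40% stopping costs about 3 to 11 percentage points of apparent worsening. Arm differences of 10 to 20 points move a null hazard ratio to about 1.06 to 1.12. These are illustrations, since the plan gives no stopping rates.

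The consequence is modest and confined to two secondary endpoints, first worsening and recovery, the latter in the opposite direction. A reader might also infer that censoring at the last entry restores the true hazard ratio. It does so only when stopping is unrelated to symptoms, and in a tolerability trial that cannot be assumed.

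**What to change.** In SAP 7.3.4, keep the present censoring dates and add one. Censor a subject without the event at the earliest of:

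- (a) Day 10 for first worsening, or Week 8 for recovery;
- (b) discontinuation of study treatment;
- (c) for recovery only, the switch to a listed GI medication;
- (d) the last day with a GSRS entry.

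The wording must say the earliest of these. Replacing the rule with the last entry alone would delete (b) and (c).

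Add one sensitivity analysis, because (d) assumes that stopping is unrelated to symptoms and does not settle gaps between entries. Interval censoring between recorded days would address the gaps. Counting diary stopping as worsening would test symptom-related stopping for the first-worsening endpoint. Name the chosen one in the SAP before unblinding.

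The cost is SAP wording and derivation code. No new data are needed.

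### Both Cox models use whole-day times with built-in ties and no stated tie method; under Breslow the hazard ratio shrinks and the test is conservative, strongly for recovery and to an unknown degree for first worsening

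*Combined protocol and SAP*

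**What the plan says.** SAP 7.3.4 defines two time-to-event secondary endpoints.

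- **First worsening** is "the number of days from Day 0 to the first date with a worsened GSRS score". Without a worsening, "his/her time to first worsening will be censored at Day 10 or the day of study treatment" discontinuation, whichever is earlier. The diary is daily, so events can fall only on Days 1 to 10. The analysis is Kaplan-Meier plus "the Cox's proportional hazards model adjusted for age, weight and baseline GSRS score".
- **Recovery** "is defined as the date of recovery minus the date of the last occurrence of the worst score", again in whole days. For a subject who never worsens, "the last occurrence of the worst score is Day 0 and time to recovery is 1". The analysis is Kaplan-Meier plus a Cox model, with no covariates named.

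No tie method appears for either model. SAP 7 states that SAS "will be used for all summaries and statistical analyses". SAP 7.3.3 gives example code, the test and the interval type for the primary logistic model; nothing comparable exists for the Cox models. The only fallback concerns first worsening: "If the proportionality assumption does not hold, a log-rank test will be used".

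**The concern.** The Cox partial likelihood assumes continuous time, and tied event times need a stated treatment. The Breslow approximation is adequate when ties are few. When a large share of the risk set fails on one day, it pulls the log hazard ratio toward 0 and gives a standard error larger than the estimator's true variability. The test then rejects too rarely under the null and loses power under an effect.

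Heavy ties are expected here. First worsening has at most ten distinct event times, and the recovery rule itself places every never-worsened subject at 1. At stake are the hazard ratio and p-value for two secondary endpoints, in a trial that SAP 5 closes at about 60 dosed patients rather than the 118 planned. The choice also stays open while SAP 5 provides for group-level review of results after Day 10.

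**Working it through.** **1. The plan's own figure.** The documents give no power, hazard ratio or event count for either Cox endpoint. The only stated figure is the primary-endpoint sample size in SAP 6: 40% v 70% improving, 80% power, two-sided 5%, 15% discontinuation.

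- Uncorrected: [1.96·√(2·0.55·0.45) + 0.84·√(0.4·0.6 + 0.7·0.3)]² / 0.3² ≈ 42 per arm.
- With continuity correction: 49 per arm; 49/0.85 gives 58 per arm, total 116, close to the planned 118.

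These rates were used to calibrate the daily scores below, reading 40% improving as 60% worsening on the 10-day average for placebo and 30% for montelukast. That reading is an assumption.

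**2. Mechanism, without simulation.** Take one day with n at risk, split equally, and d events. Breslow null information is d/4. The true (hypergeometric) variance of the score is (d/4)·(n−d)/(n−1). The ratio is (n−1)/(n−d), so a nominal 5% test effectively uses the cut-off 1.96·√[(n−1)/(n−d)]. With n = 60:

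| d on that day | Ratio | Cut-off | Actual size |
|---|---|---|---|
| 6 | 59/54 = 1.09 | 2.05 | 4.1% |
| 12 | 59/48 = 1.23 | 2.17 | 3.0% |
| 20 | 59/40 = 1.48 | 2.38 | 1.7% |
| 30 | 59/30 = 1.97 | 2.75 | 0.6% |
| 40 | 59/20 = 2.95 | 3.37 | 0.08% |

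Later, less tied days dilute this. The direction is fixed; the amount follows the Day 1 tie share.

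**3. Simulation at the planning rates.** Whole-day times, 2,000 to 4,000 trials per setting, Wald tests, days exchangeable (no drift), within-subject correlation 0.3, 0.5 and 0.8. Power, Breslow to Efron:

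| Endpoint | Correlation | 30 per arm | 59 per arm |
|---|---|---|---|
| First worsening | 0.3 | 27% to 47% | 54% to 75% |
| | 0.5 | 37% to 57% | 73% to 87% |
| | 0.8 | 47% to 66% | 83% to 93% |
| Recovery | 0.3 | 16% to 41% | 44% to 71% |
| | 0.5 | 27% to 53% | 58% to 82% |
| | 0.8 | 38% to 63% | 73% to 91% |

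- *Recovery*, over all calibrated settings (41-73% tied at 1): Breslow size 0.05-2.7%, power loss about 17-36 points. Hazard ratio 1.54 v 1.76 at correlation 0.5, 30 per arm.
- *First worsening*, no drift (32-59% tied on Day 1): Breslow size 0.5-2.8%, hazard ratio 0.62 v 0.55. A covariate-adjusted check at 30 per arm (800 trials) gave size 0.25% and 2.6% (Efron 5.1% and 5.0%) and power 45% v 65%.

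**4. First worsening when Day 1 is less crowded.**

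- Autocorrelation and no-change days, no drift: size 1.4-3.2%, loss 6-14 points.
- Upward drift added: size 2.5-4.3%, hazard ratio 0.53 v 0.50, loss 2-8 points.
- Constant daily hazard, 60% worsened by Day 10: size 3.5%, hazard ratio 0.52 v 0.51, loss 2-3 points.

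A separate grouped proportional-hazards simulation (true hazard ratio 0.50, 30 per arm) brackets this. With half of placebo worsening on Day 1, power is 48% v 64% and size 1.5% v 5.7%. With 60% worsening evenly over ten days, power is 41% v 44% and size 4.2% v 5.7%.

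**5. Recovery and the choice of tie method.** Let p be the share who never worsen and q the daily chance of recovery for the rest. The share tied at 1 is p + (1−p)q. Null rejection at 30 per arm, same p in both arms:

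| p | q | Tied at 1 | Breslow | Efron | Log-rank |
|---|---|---|---|---|---|
| 10% | 0.1 | 19% | 3.9% | 5.1% | 5.4% |
| 20% | 0.1 | 28% | 3.3% | 5.3% | 5.8% |
| 20% | 0.3 | 44% | 1.4% | 5.2% | 5.6% |
| 20% | 0.6 | 68% | 0.1% | 3.7% | 5.2% |
| 70% | 0.3 | 79% | 0.0% | 3.3% | 6.2% |
| 70% | 0.6 | 88% | 0.0% | 1.7% | 6.0% |

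At 75-90% tied, Efron is itself conservative (1.7-4.1% over both sample sizes). The log-rank test, which uses the hypergeometric variance of step 2, stays at about 5-6%. With p = 70% v 40% and q = 0.6 (82% tied), power is 0.05% for Breslow, 14% for Efron and 20% for log-rank. With q = 0.1 (59% tied) it is 14%, 38% and 33%, so the discrete test is not uniformly the more powerful.

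**The case against.** The strongest reply is that the size is not established for both models. A reader might infer that both tests run far below 5% and lose much of their power. The documents do not support that for first worsening, because they give no daily worsening rates. Two design features argue against a Day 1 pile-up: Day 0 is tied to reaching the symptom threshold (SAP 2.1), so later scores may fall back, and the DMF dose steps up after 7 days (protocol 5.3), which could move some worsening later. Even with 33% of placebo worsening on Day 1 and 90% by Day 10, one grouped-hazards model lost only 4-7 points. This stands, and the loss is therefore given as a range.

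A reader might also infer that Breslow will certainly be used. The SAP names SAS but no procedure or option, and the primary-model code is only an example. That Breslow is the default is software knowledge, so the consequence is conditional. The unspecified choice is not.

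A third inference, that a real effect would usually be missed because of ties, goes too far. At 59 per arm, Breslow power for first worsening is 54-83% in step 3. At 30 per arm, Efron itself reaches only 47-66% there and 41-63% for recovery, so the early close is also a major cause.

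Finally, many recovery ties are values assigned by the SAP rather than grouped continuous times, so a tie option does not answer whether that rule is sensible. That also stands. It is a further question and does not remove the need for a tie method. The log-rank fallback does not help: ties do not trigger it, and recovery has none.

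**Conclusion.** The point holds in conditional form. SAP 7.3.4 fits Cox models to two heavily tied whole-day endpoints without a tie method. If Breslow is applied, both hazard ratios move toward 1 and both tests are conservative.

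- **Recovery:** large when about 40-75% of subjects tie at 1, by the figures in step 3. Small (size 3.3-3.9%) only if few subjects never worsen and recovery is slow.
- **First worsening:** about 2-8 points (size 2.5-4.3%) if worsening is spread out or drifts upward; up to about 15-20 points at 30 per arm (size about 0.5-2.8%) if about a third to a half or more first worsen on Day 1. The documents cannot settle where in this range the trial lies.

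The figures rest on the Breslow assumption, on reading 40% improving as 60% worsening, and on illustrative daily-score models. The error creates no false positives, concerns two of nine secondary endpoints with no power claim attached, and leaves the primary analysis untouched. It merits a change because a better method is available at almost no cost.

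**What to change.** In SAP 7.3.4, pre-specify for both endpoints either the exact or discrete tie method or a discrete-time complementary log-log model by day. Keep the covariates already planned for each: age, weight and baseline GSRS for first worsening, none named for recovery. Report that model's hazard ratio with its likelihood-ratio p-value. The discrete (conditional logistic) form estimates an odds ratio, so choose the exact or complementary log-log form if a hazard ratio is wanted.

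Efron is acceptable for first worsening, where its size was 3.7-5.6% in every scenario of steps 3 and 4 run at the planning rates or as stress tests. A reader might take it as sufficient for both endpoints; step 5 shows that it is itself conservative for recovery when most times tie at 1, so use the exact or discrete form there.

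The cost is one line of code and a slightly less familiar model. No data, visits or patients are added.
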